11. If a local serum pregnancy test is not available or results cannot be received within 4 hours of sampling at the investigative site then a urine pregnancy test may be utilized locally to obtain timely results for randomization. All female subjects of childbearing potential will have a serum pregnancy test performed by the central laboratory.
12. Obtain a set of aerobic and a set of anaerobic samples from two separate venipuncture locations at Screening. Upon knowledge of a positive culture for a pathogen, blood cultures should be repeated until sterile (i.e., both sets of cultures from two separate venipuncture sites are negative for pathogens) through the FU visit. Await results before drawing additional sets of blood cultures. If baseline cultures are negative, follow-up cultures should be obtained only if clinically indicated (e.g., signs and symptoms of persistence, relapse, or new infection).
13. Collected from a mid-stream urine specimen, a newly-placed urinary catheter, suprapubic aspiration, or a properly disinfected collection port.
Urine cultures should be processed using a calibrated loop to identify a quantitative count of bacteria at a lower limit of 10^3 CFU/mL. The colony count and pathogenic microorganism(s) identification will be recorded and the purified isolate(s) will be sent to the central laboratory where species confirmation and antimicrobial susceptibility testing will be performed.
14. Document any adverse events that occur from the signing of informed consent through study completion. Prior conditions should be documented as medical history
15. Expected treatment duration is seven days unless clinical failure occurs earlier; maximum treatment duration is ten days (total IV and PO). The 24-h interval between IV doses can be shortened (but not prolonged) by up to 2-h (i.e., interval of 22-h to 24-h) from the first dose during doses 1-3 to adapt to a normal hospital schedule. After the third dose, the permitted IV administration window is $q24h \pm 90$ minutes. At a minimum, the first five IV doses must be administered in an in-patient hospital setting; subsequent doses may be administered on an out-patient basis. Contact Medical Monitor for dosing beyond 7 doses.
16. Subjects should receive 7-10 days of treatment. Specific criteria for determining length of treatment are described in Section 11.3.3.
17. Please refer to Section 24 for schedule of plasma PK sample collection on Day 1, Day 2, and Day 5.

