9.4 Expected Duration of Subject Participation

The expected study duration for any given subject is approximately 4 weeks. Foreseen treatment duration at study entry should be a minimum of five IV doses. The study drug may be discontinued at the discretion of the Investigator at any time. Study drug treatment should be stopped when there is treatment failure or the maximum allowed number of 10 doses has been reached.

Each subject will receive 7-10 doses of study drug (total IV and PO), including at least 5 IV doses. Visits will be conducted at Day 5, EOI, and EOT. The TOC visit will be 14-17 days after randomization, and the FU visit will be 21-28 days after randomization.

The individual subject study timeline is shown in Table 2 below.

Table 2: Timeline for Individual Study Subjects

Screening	Randomization	Study Drug Treatment	Day 5 Visit	End of IV (EOI) Visit	End of Treatment (EOT) Visit	Test of Cure (TOC) Visit	Follow-up (FU) Visit
Within 36-h prior to Randomization		Dose Cycles 1-10	5 days after Randomization	Within 1 day of Last IV Dose	Within 1 day of Last Dose (IV or PO)	14-17 days after Randomization & ≥ 5 days after last dose	21-28 days after Randomization
Establish diagnosis of cUTI Verify eligibility for enrollment Collection of a urine sample for urinalysis and culture Baseline assessment Informed consent must be obtained prior to performing any study specific procedures that are not standard of care	Use IWRS to randomize subject to study drug	Either: Eravacycline 1.5mg/kg IV plus placebo IV q24h with optional transition to Levofloxacin 750 mg PO QD OR Ertapenem 1 g IV plus placebo IV q24h with optional transition to Levofloxacin 750 mg PO QD	Assessments of clinical response and safety Collection of a urine sample for urinalysis and culture Determination of length of treatment; subjects are expected to receive 7-10 days of therapy.	Subjects are to receive at least 5 doses of IV study drug Assessments of clinical response and safety Collection of a urine sample for urinalysis and culture	Subjects are expected to receive 7-10 doses of study drug Assessments of clinical response and safety Collection of a urine sample for urinalysis and culture	Return to Study Center for: Assessment of clinical response and safety Collection of a urine sample for urinalysis and culture	Return to Study Center for: Assessment of clinical response and safety Collection of a urine sample for urinalysis and culture

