11.2.8 Follow-up Visit

The FU visit will occur 21-28 days after randomization. The following will be performed at the FU visit:

1. Clinical Assessments:

- Record signs and symptoms related to cUTI
- Complete physical exam
- Record temperature (oral, rectal, tympanic, or by temporal artery)
- Resting vital signs
- Concomitant medications
- Hematology/ chemistry safety laboratory tests
- Coagulation panel
- Urinalysis
- Blood cultures

NOTE: Upon knowledge of a positive culture for a pathogen, blood cultures should be repeated until sterile (i.e., both sets of cultures from two separate venipuncture sites are negative for pathogens) through the FU visit. If the most recently obtained blood cultures are negative, follow-up cultures should be obtained only if clinically indicated (eg, signs and symptoms of persistence, relapse, or new infection).

- Urine cultures
- AE assessment
- Clinical outcome assessment

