13.1 Definitions

13.1.1 Adverse Event

An adverse event is any adverse experience in a subject administered a pharmaceutical product, whether or not it is considered drug-related, that occurs during a subject's study participation (defined as after the time of initial informed consent). This would include any side effect, injury, toxicity, sensitivity reaction, or intercurrent illness. A pre-existing condition is one that is present at study entry and is reported as part of the subject's medical history. It should be reported as an AE if the frequency, intensity, or character of the condition worsens during study drug treatment. Subjects should be instructed to report all AEs to the Investigator or study staff. Adverse events must be appropriately documented in the subject's original source documents and entered into the eCRF. Investigators should report syndromes rather than list symptoms.

Events that result from lack of efficacy of study drug (eg, treatment failure) are not considered AEs.

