13.1.3 Serious Adverse Event (SAE)

An SAE is any AE, occurring at any dose and regardless of causality that:

- Results in death
- Is life-threatening. Life-threatening means that the subject was at immediate risk of death from the reaction as it occurred (i.e., it does not include a reaction which hypothetically might have caused death had it occurred in a more severe form)
- Requires in-patient hospitalization or prolongation of existing hospitalization. Hospitalization admissions and/or surgical operations scheduled to occur during the study period, but planned prior to study entry, are not considered AEs if the illness or disease existed before the subject was enrolled in the trial, provided that it did not deteriorate in an unexpected manner during the study (eg, surgery performed earlier than planned)
- Results in persistent or significant disability/incapacity. Disability is defined as a substantial disruption of a person's ability to conduct normal life functions
- Is a congenital anomaly/birth defect
- Is an important medical event. An important medical event is an event that may not result in death, be life-threatening, or require hospitalization but may be considered an

SAE when, based upon appropriate medical judgment, it may jeopardize the subject and may require medical or surgical intervention to prevent one of the outcomes listed in the definitions for SAEs. Examples of such medical events include allergic bronchospasm requiring intensive treatment in an emergency room or at home, blood dyscrasias or convulsions that do not result in in-patient hospitalization, or the development of drug dependency or drug abuse

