13.2 AE Collecting and Reporting

All AEs spontaneously reported by the subject and/or in response to an open question from study personnel or revealed by observation, physical examination or other diagnostic procedures will be recorded on the appropriate page of the eCRF starting from the time of initial informed consent. Any clinically relevant deterioration in laboratory assessments or other clinical findings is considered an AE and must be recorded on the appropriate pages of the eCRF starting from the time of initial informed consent. When possible, signs and symptoms indicating a common underlying pathology should be noted as one comprehensive event.

All SAEs that occur during the course of the study, as defined by the protocol, must be reported by the Investigator to the Sponsor or its pharmacovigilance designee/contract research organization (CRO) within 24-h from the point in time when the Investigator becomes aware of

the SAE. In addition all SAEs, including all deaths, which occur from the time of signing of the informed consent up to and including 30 days after administration of the last dose of study drug, must be reported to the Sponsor or its designated CRO within 24-h. All SAEs and deaths must be reported whether or not considered causally related to the study drug. The information collected will include a minimum of the following: subject number, a narrative description of the event, and an assessment by the Investigator as to the severity of the event and relatedness to study drug. Follow-up information on the SAE may be requested by the Sponsor or its representative CRO. Detailed instructions for the collecting and reporting of SAEs will be provided in the Investigator Site File.

If there are serious, unexpected ADRs associated with the use of the study drug, appropriate regulatory agencies, all participating Investigators, as well as central IRBs/IECs will be notified on an expedited basis (7 days for fatal or life-threatening serious, unexpected ADRs). Local IRBs/IECs will be notified of all unexpected, serious ADRs involving risk to human subjects in accordance with the rules and regulations of the local IRB/IEC. Details of reporting responsibilities will be outlined in the study-specific Safety Management Plan.

An unexpected event is one that is not reported in the IB or the relevant prescribing information.

Reporting of SAEs and Suspected Unexpected Serious Adverse Reactions (SUSARs)

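### The adverse event rule for pre-existing conditions stops at the end of treatment, while the protocol's other collection rules run to Follow-up or beyond

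*Protocol*

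**What the plan says.** Protocol 13.1.1 treats a condition present at study entry as medical history and then says when it becomes an adverse event: "It should be reported as an AE if the frequency, intensity, or character of the condition worsens during study drug treatment". No other sentence in the protocol says when a medical-history condition becomes an AE.

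The surrounding text uses wider windows:

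- The general definition in the same paragraph covers any adverse experience "that occurs during a subject's study participation (defined as after the time of initial informed consent").
- Section 3, footnote 14: "Document any adverse events that occur from the signing of informed consent through study completion". The footnote then directs that prior conditions go into medical history, and does not mention worsening.
- Protocol 13.2: "Any clinically relevant deterioration in laboratory assessments or other clinical findings is considered an AE and must be recorded", counted from informed consent and with no limit to the dosing period.
- Protocol 13.2 requires SAEs to be reported "up to and including 30 days after administration of the last dose of study drug".
- Protocol 15.2.2 and SAP 5.8.1 count as treatment-emergent any AE that appears or worsens once study drug has started. Neither sets an end date.

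**The concern.** Section 13 asks staff to report events that satisfy the AE or SAE definition, so the definition acts as the filter at every visit. AE assessments are scheduled at EOT, TOC and FU, but they collect only what site staff believe qualifies. For a medical-history condition, the sentence in 13.1.1 is the natural test to apply, and it refers only to the time on study drug.

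This population makes the point more than academic. Protocol 11.2.2 caps pyelonephritis with normal anatomy at about 50% of enrolment. If the cap holds, about half of subjects or more enter through criterion 1b: catheter, retention, neurogenic bladder, obstruction, renal azotemia or abnormal anatomy. All of these are present at entry.

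The analysis depends on complete collection. The TEAE tables are meant to include worsening after dosing begins, but they can count only what was recorded. With about 130 sites and two windows in one paragraph, practice could also differ between sites.

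**Working it through.** The plan states no last-dose-to-Follow-up interval, so there is no figure to reproduce. The check is date arithmetic, then a comparison of the provisions.

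**Inputs**

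- Doses: "Each subject will receive 7-10 doses of study drug (total IV and PO), including at least 5 IV doses" (Protocol 9.4), given once every 24 hours.
- Follow-up: "The FU visit will occur 21-28 days after randomization" (Protocol 11.2.8).
- Assumption: dose 1 on the day of randomization (day 0). The alternative is dose 1 one day later.

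**Formula**

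Day of last dose = day of dose 1 + (number of doses − 1). Off-treatment interval = FU day − day of last dose.

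| Dose 1 | Doses | Last dose (day) | FU day 21 | FU day 28 |
|---|---|---|---|---|
| Day 0 | 7 | 6 | 21 − 6 = 15 | 28 − 6 = 22 |
| Day 0 | 10 | 9 | 21 − 9 = 12 | 28 − 9 = 19 |
| Day 1 | 7 | 7 | 21 − 7 = 14 | 28 − 7 = 21 |
| Day 1 | 10 | 10 | 21 − 10 = 11 | 28 − 10 = 18 |

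The range is 12-22 days, or 11-21 days with the later start. As a share of the time from randomization to FU, the extremes are 11/21 = 52% and 22/28 = 79%, so more than half in every case. Early stopping lengthens the interval: after 3 doses from day 0 the last dose is on day 2, giving 19-26 days.

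**What covers worsening of a pre-existing condition in that interval**

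| Type of worsening | Provision that reaches it | Still exposed? |
|---|---|---|
| Serious | 13.2: all SAEs to 30 days after last dose, whatever the cause | Largely covered |
| Laboratory | 13.2 deterioration rule; central chemistry and hematology at TOC and FU; SAP 5.8.2 shift tables, two-grade increases and worst post-baseline values | Largely covered, even if no AE is entered |
| Non-serious, clinical or symptomatic | 13.1.1 general definition, footnote 14 and the 13.2 deterioration rule call for it; the specific 13.1.1 sentence does not | Yes, if a site follows the specific sentence |

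The last row is where the conflict has consequences: two instructions point to recording and one can be read against it, and the protocol does not say which governs.

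The 30-day SAE window outlasts the FU visit. With the last dose on day 6 to day 9 it closes on day 36 to day 39. A single end date at FU would therefore be too short for serious events, which is why the fix needs a cross-reference.

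One further check concerns pharmacology. Protocol 7.3.1 gives a half-life of 29.34 h, so five half-lives are 5 × 29.34 = 146.7 h, about 6 days. Protocol 11.3.1 and 11.3.2 allow IV study drug for the whole course when no suitable oral agent is available. For a subject in that position on eravacycline, drug is still present for several days that lie outside the 13.1.1 window.

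**The case against.** The strongest reply is that the protocol already requires these events. The sentence says such worsening should be reported if it happens on treatment. It does not say only if, and nowhere does the protocol say that later worsening goes unreported. The deterioration rule in 13.2 is mandatory, starts at consent and has no treatment-period limit. TOC and FU each include AE assessment, signs and symptoms, a complete physical examination, vital signs and safety chemistry. Section 13.6 follows AEs through FU.

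Much of this stands. A reader might infer that all worsening after the last dose is excluded from reporting, and so cannot be an SAE either. The documents do not support that. Section 13.2 calls for all SAEs to 30 days after the last dose. Section 13.1.3, in its clause on planned admissions, exempts them only "provided that it did not deteriorate in an unexpected manner during the study", which judges a prior illness over the study and not over the dosing period. A reader might also infer that worsening renal or hepatic function would be lost to the analysis. It would not, because the central laboratory results at TOC and FU are analysed whether or not an AE is entered. And the 12-22 days are an off-treatment interval, not a period without reporting: new events, deteriorations and SAEs are all collected during it.

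What does not stand is that the wider provisions make the sentence harmless. They show what was intended, but footnote 14 itself sends prior conditions to medical history, and the definition of an SAE begins from that of an AE. The sentence remains inconsistent with them.

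**Conclusion.** The sentence in 13.1.1 is wrong as written. It is an internal inconsistency in a collection rule, not a planned gap in safety reporting. Applied literally, it could under-record mainly non-serious clinical worsening of pre-existing conditions over 12-22 days between last dose and FU (11-21 if dosing starts a day after randomization), assuming 7-10 daily doses and an FU visit within its window. Serious events and laboratory worsening are largely captured by other provisions.

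The number of events lost cannot be estimated. The documents give no rate for such worsening, no count of subjects with conditions outside the urinary tract, and no indication of how sites would read the sentence. Nothing in them suggests a difference between arms. Sample size, alpha and power are unaffected. The reason to act is that clinical events never entered cannot be recovered at analysis, and the correction is small.

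**What to change.** In Protocol 13.1.1, replace the limit to the treatment period with wording under which worsening counts at any time from informed consent through study completion (the FU visit). Add a cross-reference to 13.2 for serious events, whose existing window of 30 days after the last dose is unchanged. Notify sites of the clarification. It would also help for footnote 14 in Section 3 to say that worsening of a prior condition is an AE.

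The change uses windows the protocol already states, adds no visits or procedures, and needs no change to the TEAE definition in the SAP. The cost is a short protocol clarification, a notice to sites and slightly more AE records.

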13.1.2 Adverse Drug Reaction (ADR)

An adverse drug reaction (ADR) is any untoward and unintended response in a subject to an investigational medicinal product which is related to any dose administered to that subject.

13.1.3 Serious Adverse Event (SAE)

An SAE is any AE, occurring at any dose and regardless of causality that:

- Results in death
- Is life-threatening. Life-threatening means that the subject was at immediate risk of death from the reaction as it occurred (i.e., it does not include a reaction which hypothetically might have caused death had it occurred in a more severe form)
- Requires in-patient hospitalization or prolongation of existing hospitalization. Hospitalization admissions and/or surgical operations scheduled to occur during the study period, but planned prior to study entry, are not considered AEs if the illness or disease existed before the subject was enrolled in the trial, provided that it did not deteriorate in an unexpected manner during the study (eg, surgery performed earlier than planned)
- Results in persistent or significant disability/incapacity. Disability is defined as a substantial disruption of a person's ability to conduct normal life functions
- Is a congenital anomaly/birth defect
- Is an important medical event. An important medical event is an event that may not result in death, be life-threatening, or require hospitalization but may be considered an

SAE when, based upon appropriate medical judgment, it may jeopardize the subject and may require medical or surgical intervention to prevent one of the outcomes listed in the definitions for SAEs. Examples of such medical events include allergic bronchospasm requiring intensive treatment in an emergency room or at home, blood dyscrasias or convulsions that do not result in in-patient hospitalization, or the development of drug dependency or drug abuse

Clarification should be made between the terms “serious” and “severe” since the terms ARE NOT synonymous. The term “severe” is often used to describe the intensity (severity) of a specific event (as in mild, moderate, or severe myocardial infarction); the event itself, however, may be of relatively minor medical significance (such as a severe headache). This is NOT the same as “serious,” which is based on subject/event outcome or action criteria described above, and is usually associated with events that pose a threat to a subject’s life or functioning. A severe AE does not necessarily need to be considered serious. For example, persistent nausea of several hours duration may be considered severe nausea but not an SAE. On the other hand, a stroke resulting in only a minor degree of disability may be considered mild, but would be defined as an SAE based on the above noted criteria. Seriousness (not severity) serves as a guide for defining regulatory reporting obligations.

Events that result from lack of efficacy of study drug (eg, treatment failure) are not considered SAEs (eg, prolonged hospitalizations due to treatment failures will not be considered SAEs).

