10.4.1 Early Discontinuation from Study Drug Administration

If a subject prematurely discontinues from study drug treatment (including withdrawal of consent for study drug treatment), every reasonable effort should be made to adhere to future protocol evaluations and examinations as specified in the SOA. The reason for early study drug treatment withdrawal should be recorded on the appropriate page(s) of the eCRF. Reasons for withdrawal from study drug treatment may include, but are not limited to, the following:

1. Occurrence of an AE, which, in the opinion of the Investigator, warrants the subject's permanent withdrawal from study treatment. In the event of withdrawal due to the occurrence of an AE, the regional Medical Monitor must be notified within 24-h. Subjects withdrawn secondary to an ongoing non-serious AE (regardless of relationship to study drug) or SAE that is not related to study drug treatment must be followed clinically until the FU visit. Subjects withdrawn secondary to an ongoing study drug-related SAE must be followed clinically until resolution or stabilization (eg, return to baseline or no further improvement expected)
2. Insufficient therapeutic effect requiring rescue/non-study systemic antibacterial treatment for the current cUTI

If a subject has been discharged from the hospital and refuses to return to the investigational site for scheduled evaluations, but is willing to undergo follow-up investigations, clinical response

data, safety data, and concomitant medication information may be collected by telephone and/or through medical records.

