11.1.5 Clinical Outcome

Clinical outcome will be assessed at the Day 5, EOI, EOT, TOC, and FU visits. Clinical outcomes will be classified as cure, failure, indeterminate or missing based on clinical assessments. A favorable clinical outcome is “cure”.

Clinical outcomes are defined as follows:

Clinical Cure

Clinical cure is defined as complete resolution or significant improvement of signs or symptoms of the infection such that no rescue/non-study antibacterial therapy is required to treat the cUTI that presented at study entry.

Clinical Failure

Subjects are assigned an outcome of clinical failure in the event of:

- Death related to cUTI at any time point
- Persistence of clinical symptoms of cUTI or new symptoms have developed
- Initiation of rescue/non-study antibacterial drug therapy for cUTI

Indeterminate

Study data are indeterminate if the outcome is other than clinical cure or clinical failure. The reason for an “indeterminate” designation must be provided.

Missing

Study data are listed as “missing” if the Investigator did not complete an assessment or if the subject did not complete the study visit.

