15.4 Data Safety Monitoring Board (DSMB)

A DSMB will meet after approximately 300 subjects have reached EOT in the study, and again after approximately 800 subjects have reached EOT. The DSMB will advise the Sponsor regarding the continuation, modification, or termination of the study. The DSMB may meet at other timepoints as necessary.

The DSMB will have access to the following data:

- Incidence of AEs (overall and drug-related)
- Listing of SAEs
- Premature discontinuations from study drug due to an AE
- Safety laboratory data

The DSMB may be provided with additional data if requested.

The DSMB and Sponsor will conduct an assessment of the actual number of subjects in the micro-ITT population, which will be made following the completion of treatment (EOT) of approximately 800 subjects. If there is less than the expected proportion of subjects in the micro-ITT population, the sample size will be adjusted as needed (without a formal protocol amendment) to provide a sufficient number of evaluable subjects.

In addition, the DSMB will conduct an assessment of the overall (aggregated across treatment groups) blinded responder rate (clinical cure and microbiological success) at the TOC visit following the completion of approximately 800 subjects. If the overall blinded responder rate is less than the rate used in the sample size calculation for the eravacycline group, the sample size will be increased as needed (without a formal protocol amendment) to ensure 80% power. The sample size will not be decreased if the overall blinded responder rate is greater than the rate used in the sample size calculation.

A charter for the DSMB, comprised as a separate document, will be available prior to the first meeting. Recommendations from the DSMB will be made in writing and provided to the Sponsor after each data review.

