5.8. Safety Analyses

5.8.1. Adverse Events

Verbatim descriptions of AEs will be coded using Version 20.0 of MedDRA. Summary tables will be provided for all treatment-emergent AEs (TEAEs). A TEAE is defined as any AE that newly appeared, increased in frequency, or worsened in severity following initiation of study drug. An AE is considered treatment emergent if the AE starts on or after the first dose of study drug. In addition, all AEs (including non-TEAEs), serious TEAEs, and TEAEs leading to study drug discontinuation will be provided in listings by treatment group, site, subject, verbatim term, MedDRA SOC and preferred term, start and end date, seriousness flag, severity, relationship to study drug, action taken with study treatment, frequency and outcome. All AEs will be coded using the MedDRA coding system and displayed in tables and data listings using SOC and preferred term.

An overall summary of AEs will include number and percentage of subjects in each treatment group who experienced at least 1 AE of the following categories: any AE, any TEAE, any drug-related TEAE (defined as possibly, probably or definitely related to study drug), any severe TEAE, any serious TEAE (SAE), any drug-related SAE, any SAE leading to death, any TEAE leading to premature discontinuation of study drug, and any SAE leading to premature study drug discontinuation.

The number and percentage of subjects reporting a TEAE in each treatment group will be tabulated by SOC and preferred term; by SOC, preferred term, and severity (mild, moderate,

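### Serious non-fatal treatment failures fall outside AEs, SAEs and the listed DSMB data, and the classification of fatal failures is contradictory

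*Protocol*

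**What the plan says.** Protocol 13.1.3 opens broadly: "An SAE is any AE, occurring at any dose and regardless of causality that" meets one of the seriousness criteria. Hospitalization, its prolongation and life-threatening events are among those criteria. The section closes with the exclusion "Events that result from lack of efficacy of study drug (eg, treatment failure) are not considered SAEs", and gives as its example that "prolonged hospitalizations due to treatment failures will not be considered SAEs". Protocol 13.1.1 applies the same exclusion one level down: "Events that result from lack of efficacy of study drug (eg, treatment failure) are not considered AEs".

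On deaths, Protocol 11.1.5 makes "Death related to cUTI at any time point" a clinical failure. Protocol 13.2 requires every death up to 30 days after the last dose to be reported within 24 hours and speaks of deaths as included among the SAEs. Protocol 13.4 has the cause of death entered as the AE. In SAP 5.8.1 the overall AE summary counts deaths through the row "any SAE leading to death", and the SAP plans no separate table of all-cause deaths.

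Protocol 15.4 lists four kinds of data for the DSMB: AE incidence, an SAE listing, "Premature discontinuations from study drug due to an AE", and safety laboratory data. More may be supplied on request. Protocol 10.4.1 treats "Insufficient therapeutic effect requiring rescue/non-study systemic antibacterial treatment for the current cUTI" as a reason for stopping study drug that is separate from an AE. The board also assesses the responder rate at TOC, pooled across arms and blinded, once about 800 subjects have completed. SAP 1.2.2 states that there are no formal stopping rules.

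**The concern.** For an anti-infective, the serious harm most directly tied to the randomized drug is an infection that is not controlled. A site that follows 13.1.1 and 13.1.3 literally would record a subject who worsens to a life-threatening state, or is readmitted, because study drug failed as a clinical failure and nothing more. That subject is then missing from the AE incidence, the SAE listing and the AE discontinuations, and so from three of the four items the DSMB is due to receive. If failures are more frequent in one arm, that arm also loses more serious events from the SAE comparison, which flatters it. The first safety reason for termination in Protocol 11.5 is framed in terms of AEs and carries the same gap.

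For deaths the problem is different. The texts point in opposite directions, so two sites could classify the same cUTI death differently, and whether it enters the SAP summary would depend on the site.

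**Working it through.** **1. Where each event goes**

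| Event attributed to lack of efficacy | Protocol 13.1.1 / 13.1.3 | Other text | In the 15.4 list? |
|---|---|---|---|
| Life-threatening progression or readmission | Neither AE nor SAE | Clinical failure if symptoms persist or rescue starts (11.1.5) | No |
| Longer hospital stay | Excluded by name | Prolongation is itself a seriousness criterion (13.1.3) | No |
| Stopping study drug for insufficient effect | Not an AE | Separate reason in 10.4.1 | No |
| Death from cUTI | Neither, because 11.1.5 makes it a failure | Reported with the SAEs (13.2); cause entered as the AE (13.4) | Cannot be determined |

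For the non-fatal rows the text is consistent in form: an SAE must first be an AE, and 13.1.1 has already removed the event. The result is a gap. Only the last row is a contradiction.

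**2. The plan's own figures (context only)**

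Inputs from Protocol 15.3: 71% and 72% at TOC, 93% and 94% at EOI, margin 10%, one-sided alpha 0.025, power 80%, micro-ITT share 66%.

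- Simple unpooled formula: n per arm = (z₀.₉₇₅ + z₀.₈₀)² × [p₁(1−p₁) + p₂(1−p₂)] / (p₁ − p₂ + 0.10)² = 7.849 × (0.2059 + 0.2016) / 0.09² = 394.9, so 395.
- Farrington-Manning gives 394.2, also 395, as stated.
- 790 / 0.66 = 1197, about 1200.

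The point does not rest on these numbers. They confirm that the inputs used below were read correctly.

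**3. What the pooled responder rate can show**

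With 1:1 allocation, pooled rate = (eravacycline rate + ertapenem rate) / 2.

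| Eravacycline | Ertapenem | Pooled | Difference |
|---|---|---|---|
| 70.5% | 71.5% | 71% | −1 point |
| 66% | 76% | 71% | −10 points |
| 61% | 81% | 71% | −20 points |

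All three give the 71% trigger value in SAP 4.7, so none would change the sample size, and the board could not tell them apart. No efficacy figure is listed for the meeting at about 300 subjects.

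**4. Possible size**

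At the 800-subject review there are about 400 subjects per arm.

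- Expected subjects with an SAE, at the rates of the earlier phase 3 cUTI study (Protocol 7.3.6): 400 × 0.015 = 6.0 on eravacycline; 400 × 0.013 = 5.2 at that study's comparator rate.
- The documents give no rate of serious failure. Assumed range: 0.5%, 1%, 2%, 3%. This gives 400 × 0.005 = 2, then 4, 8, and 400 × 0.03 = 12 subjects.
- Relative to 6 expected: 2/6 = 0.3 up to 12/6 = 2.0.

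**The case against.** Several points count against a broad reading, and most of them stand.

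- **Deaths.** A reader might infer that a cUTI death leaves no SAE record and that the DSMB would not see deaths. The documents do not support that. Protocol 13.2 counts deaths with the SAEs, 13.4 gives each a recorded AE term, and the synopsis says deaths will be identified. Fatal failures probably reach the SAE listing. What remains is that 13.1.1 and 13.1.3 say otherwise.
- **The board is not blind to everything.** It sees a pooled responder rate, may meet at other times and may request data. A low pooled rate could prompt a request. The charter is a separate document and may already cover failures. This stands, but the pooled rate comes once, late, and without arms.
- **Some sites may report anyway.** Protocol 13.2 also calls a clinically relevant deterioration in clinical findings an AE. That could lead a site to report a serious failure despite the exclusion, so the counts above assume sites follow 13.1.1 and 13.1.3.
- **Failures are not lost.** Clinical failure and rescue feed the primary endpoint. The SAP tabulates reasons for non-response, reasons for discontinuation and systemic antibacterials by arm. These tables come at study end and do not mark which failures were serious.
- **The earlier cUTI study.** A reader might take its result (60.4% versus 66.9%; difference −6.5, 95% CI −14.1 to 1.2) as evidence that excess failure is to be expected here. Protocol 7.3 and 7.3.6 attribute it to low exposure on oral eravacycline. That explanation is post hoc, but this trial uses no oral eravacycline, so the result does not carry over directly.
- **Size.** Applying that 6.5-point deficit to the 800-subject review gives 400 × 0.66 × 0.065, about 17 extra non-responders. It is tempting to read these as hidden serious harm. They are failures of a composite endpoint, and a clinically cured subject with a persistent urine pathogen counts among them (SAP Table 5). They would also enter the pooled rate.

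**Conclusion.** The point holds in a limited form. By the protocol's wording, non-fatal serious outcomes attributed to lack of efficacy are outside AEs and SAEs, and nothing in the listed DSMB data would show an excess of them in one arm. Fatal failures are covered by two sets of sections that disagree, and the SAP's death count depends on which one a site follows.

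On an assumed serious-failure rate of 0.5% to 3%, 2 to 12 subjects per 400 would be left out, or 0.3 to 2 times the 6 subjects per arm expected to have an SAE on eravacycline. That range is an assumption. The SAE benchmark is borrowed from a study with a different comparator, and the documents do not say whether that study used the same exclusion. The conclusion also assumes that the DSMB charter adds nothing to the 15.4 list.

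The primary efficacy analysis is unaffected, because failures are counted there. It would be wrong to conclude that deaths go unreported or that the board has no view of failure at all.

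**What to change.** 1. **Reconcile the death wording.** Bring Protocol 13.1.1 and 13.1.3 into line with 13.2 and 13.4 so that every death has one stated classification. Add a seriousness flag to clinical failures on the eCRF so that serious failures can be tabulated by arm. The SAE reporting definition for non-fatal failures need not change.
2. **Extend the DSMB data.** In Protocol 15.4 and the charter, add by-arm all-cause deaths, clinical failures with the seriousness flag, starts of rescue antibiotics, and discontinuations for insufficient therapeutic effect. State that they are reviewed for harm only, with no efficacy test. Keep the sample-size step on pooled blinded data and have a blinded statistician run it. The SAP 4.7 argument for no alpha adjustment rests on that review being aggregated, and it should not be done by a board holding by-arm failure counts.
3. **Extend the SAP.** In SAP 5.8.1, add all-cause deaths by arm, whether or not recorded as an SAE.

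The cost is a few more DSMB tables, largely from data already collected, one eCRF field, and wording changes in the protocol, charter and SAP. The real trade-off is that Protocol 9.1 and 15.4 currently give the pooled responder-rate step to the DSMB, and it would move to a blinded statistician.
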